|              | 16. Evaluate the safety and tolerability of dabrafenib in combination with trametinib versus carboplatin with vincristine.   |
|              | 17. Evaluate the palatability of dabrafenib oral suspension and trametinib oral solution   |
|              | 18. Characterize the pharmacokinetics of dabrafenib, its metabolites and trametinib in the study population.   |
|              | 19. Assess patient reported outcomes of dabrafenib in combination with trametinib versus carboplatin with vincristine.   |
| Study design | CDRB436G2201 combines two pediatric glioma cohorts into a single multi-center, global, open-label, phase II study. The HGG cohort is a single arm part evaluating the effect of dabrafenib in combination with trametinib in children and adolescent patients with BRAF V600 mutation positive relapsed, refractory HGG. Approximately 40 patients will be enrolled to receive oral dabrafenib twice daily and trametinib once daily based on weight, age and appropriate dose level.   |
|              | The LGG cohort is a randomized part comparing the anti-tumor activity of dabrafenib in combination with trametinib to the combination of carboplatin and vincristine in children and adolescents with BRAF V600 mutation positive LGG. Approximately 102 patients will be randomized in a 2:1 ratio to either dabrafenib plus trametinib or carboplatin with vincristine. For the LGG cohort, patients randomized to carboplatin with vincristine control arm will be allowed to crossover to receive dabrafenib in combination with trametinib treatment after centrally confirmed and RANO-defined disease progression. |
|              | All patients will be followed for survival for at least 2 years after the last patient first study treatment (except if consent is withdrawn, patient death, lost to follow-up or study is discontinued). An interim analysis for futility for the HGG cohort will be implemented to allow possible termination of recruitment into the HGG cohort in the event that there is insufficient efficacy. An independent DMC will be instituted to review safety data during the study for all patients in LGG and HGG cohorts. For full details of study design refer to Section 4.  |
| Population   | This study will be conducted in two cohorts of pediatric patients, HGG cohort and LGG cohort.  |

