### 1.2.3.1 Safety of dabrafenib with trametinib

Twelve patients were treated in part C dose exploration for combination therapy of dabrafenib with trametinib, 3 at 50% dabrafenib, and 9 at full dose dabrafenib. Each received full dose trametinib.

All twelve patients had *BRAF* V600 mutant LGG. Two (17%) had independently confirmed PR as best response, 8 (67%) had SD, and 2 (17%) had PD as best response. Eight (67%) remain on treatment, with median treatment duration at 41 weeks at the time of interim analysis.

The most common AEs reported, regardless of causal relationship were rash (67%), pyrexia (58%), diarrhea, fatigue, headache, and vomiting (each 42%). Two patients had a total of 5 possibly related SAEs, both with ejection fraction decrease (17%) and one each with nausea, vomiting, and pyrexia (8%). Dose interruptions for toxicity were required for 8 (67%) patients. There have been no deaths in this group.

No dose limiting toxicities were observed. Evaluation of combination therapy in patients under 6 years of age also demonstrates tolerability at the 100% dose of trametinib (0.032 mg/kg/day) together with 100% dabrafenib dose (5.25 mg/kg/day divided into two equal doses per day).

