#### 6.3.1.1 Pyrexia

Episodes of pyrexia syndrome have been observed in patients receiving dabrafenib monotherapy or in combination with trametinib. The pyrexia syndrome is defined as treatment-related fever (≥38°C) or chills/rigors/night sweats or flu-like symptoms. In a minority of cases pyrexia was accompanied by symptoms such as severe chills/rigors, dehydration, and hypotension, dizziness or weakness and required hospitalization. The incidence and severity of pyrexia syndrome are increased when dabrafenib is used in combination with trametinib compared to dabrafenib monotherapy.

Patients and guardians must be instructed on the importance of immediately reporting febrile episodes. Dabrafenib and trametinib must be interrupted promptly and anti-pyretics (acetominophen, ibuprofen, similar) started at the very first symptom of pyrexia or its associated prodrome (chills or rigors or night sweats or flu-like symptoms). Adequate hydration status should be maintained. Dabrafenib and trametinib should be restarted upon improvement of symptoms of at least 24 hours, and at the same dose.

In the event of recurring pyrexia events despite the use of antipyretics and drug interruption, the use of oral corticosteroids may be considered when restarting dabrafenib and trametinib. In patients experiencing pyrexia associated with rigors, severe chills, dehydration or hypotension, serum creatinine increase and other evidence of renal function decrease should be monitored carefully during and following severe events of pyrexia.

Pyrexia accompanied by hypotension, dehydration requiring intravenous fluids, renal insufficiency and/or severe (≥ Grade 3) rigors/chills in the absence of an obvious infectious cause are to be reported as a SAE.

Guidelines for dose modification and management for pyrexia syndrome considered to be related to dabrafenib are provided in Table 6-16.

Table 6-16 Mandatory dose modification and recommended clinical management for pyrexia syndrome suspected to be related to dabrafenib and/or trametinib treatment

| Pyrexia   |   |   |  |
|---|---|---|--|
| Occurrence  | Recommended adverse event management guidelines   | Mandatory dose modification requirements  |  |

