#### 6.3.1.16.5 Allergic reactions

Allergic reactions may occur in 10 to 30% of children receiving frequent carboplatin. These reactions can include facial flushing, urticaria, agitation, abdominal pain, edema, and sometimes bronchospasm leading to hypoxia and even respiratory arrest.

Patients receiving carboplatin should be monitored by an experienced nurse throughout the infusion and for 1 hour after.

Patients with any respiratory compromise as a result of carboplatin therapy should not receive carboplatin again and will be discontinued from the study. They will continue into posttreatment follow up.

Patients with mild or questionable reactions without respiratory compromise may continue on therapy with pre-treatment as per below.

Carboplatin allergies should be documented as an adverse event in the eCRF.

Carboplatin should always be given in a setting with rapid access to pediatric advanced lifesupporting support capability.

Consideration should be given to provide effective measures to prevent any recurrences of allergic reactions.

The following are offered as a supplement to institutional practice. If an allergic reaction occurs it should be treated as for any other drug reactions as follows:

- 1. Stop the carboplatin infusion
- 2. Rapid assessment and management of the airway
- 3. If airway compromise or acute bronchospasm, give Epinephrine 0.01 ml/kg (maximum 0.5 mL) of 1:1000 solution SQ and repeat in 20 minutes if necessary.
- 4. Albuterol inhaled can be used to treat resistant bronchospasm.
- 5. Diphenhydramine 1-2 mg/kg slow IV will help shorten the duration of the reaction, but does not have an immediate effect.
- 6. Glucocorticoids may have no effect for 6 to 12 hours, but may help prevent relapse of severe reactions.
- 7. Patients with mild to moderate reactions (urticaria or mild bronchospasm) should be observed for a minimum of 6 hours. Those with moderate to severe reactions may relapse and should be observed in the hospital at least overnight.
- 8. Prevention of recurrence:
  - a. Children with respiratory compromise should no longer receive carboplatin and are discontinued from the study.

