# 8.1.2 Laboratory test abnormalities

# 8.1.2.1 Definitions and reporting

Laboratory abnormalities that constitute an Adverse event in their own right (are considered clinically significant, induce clinical signs or symptoms, require concomitant therapy or require changes in study treatment), should be recorded on the Adverse Events eCRF. Whenever possible, a diagnosis, rather than a symptom should be provided (e.g. anemia instead of low hemoglobin). Laboratory abnormalities that meet the criteria for Adverse Events should be followed until they have returned to normal or an adequate explanation of the abnormality is found. When an abnormal laboratory or test result corresponds to a sign/symptom of an already reported adverse event, it is not necessary to separately record the lab/test result as an additional event.

Laboratory abnormalities, that do not meet the definition of an adverse event, should not be reported as adverse events. A Grade 3 or 4 event (severe) as per CTCAE does not automatically indicate a SAE unless it meets the definition of serious as defined below and/or as per investigator's discretion. A dose hold or medication for the lab abnormality may be required by the protocol in which case the lab abnormality would still, by definition, be an adverse event and must be reported as such.

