#### 8.2 Serious adverse events

#### 8.2.1 **Definitions**

Serious adverse event (SAE) is defined as one of the following:

- Is fatal or life-threatening
- Results in persistent or significant disability/incapacity
- Constitutes a congenital anomaly/birth defect
- Is medically significant, i.e., defined as an event that jeopardizes the patient or may require medical or surgical intervention to prevent one of the outcomes listed above
- Requires inpatient hospitalization or prolongation of existing hospitalization,
- Note that hospitalizations for the following reasons should not be reported as serious adverse events:

- Routine treatment or monitoring of the studied indication, not associated with any deterioration in condition
- Elective or pre-planned treatment for a pre-existing condition that is unrelated to the indication under study and has not worsened since signing the informed consent/assent
- Social reasons and respite care in the absence of any deterioration in the patient's general condition
- Note that treatment on an emergency outpatient basis that does not result in hospital admission and involves an event not fulfilling any of the definitions of a SAE given above is not a serious adverse event

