#### 10.5.1 Safety objectives

Safety will be assessed separately for the HGG and LGG cohorts. For the LGG cohort the data will be analyzed by treatment arm.

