#### 10.5.1.2 Adverse events (AEs)

Summary tables for adverse events (AEs) will include only AEs that started or worsened during the on-treatment period, the treatment-emergent AEs.

The incidence of treatment-emergent AEs (new or worsening from baseline) will be summarized by system organ class and/ or preferred term, severity (based on CTCAE grades), type of AE, and relation to study treatment.

Serious adverse events (SAE), non-serious adverse events and adverse events of special interest (AESI) during the on-treatment period will be tabulated.

All deaths (on-treatment and post-treatment) will be summarized.

All AEs, deaths and serious adverse events (including those from the pre and post-treatment periods) will be listed and those collected during the pre-treatment and post-treatment period will be flagged. A listing of all grouping levels down to the MedDRA preferred terms used to define each AESI will be generated.

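### Events designated as SAEs attach mainly to dabrafenib/trametinib, so the LGG by-arm SAE table can overstate that arm's SAE incidence

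*Protocol*

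**What the plan says.** **The table.** Protocol Section 10.5.1.2 states that "Serious adverse events (SAE), non-serious adverse events and adverse events of special interest (AESI) during the on-treatment period will be tabulated". Section 10.5.1 adds that "For the LGG cohort the data will be analyzed by treatment arm". The LGG objective is comparative: "Evaluate the safety and tolerability of dabrafenib in combination with trametinib versus carboplatin with vincristine". Table 3-1 lists SAE incidence within that endpoint.

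**The general definition, both arms.** Section 8.2.1 gives the usual seriousness criteria and names no event. One criterion reads "Is medically significant, i.e., defined as an event that jeopardizes the patient or may require medical or surgical intervention". For laboratory findings, Section 8.1.2.1 adds that "A Grade 3 or 4 event (severe) as per CTCAE does not automatically indicate a SAE unless it meets the definition of serious".

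**The added list.** Section 6.3.1 requires SAE reporting for named events:
- LVEF decrease, symptomatic or not (Table 6-23, titled for LVEF changes suspected to be related to dabrafenib and/or trametinib)
- retinal vein occlusion and retinal pigment epithelial detachment (RPED) (6.3.1.4)
- cutaneous squamous cell carcinoma and new primary melanoma (6.3.1.5.1)
- new non-cutaneous malignancy (6.3.1.5.2)
- treatment-related pyrexia with hypotension, dehydration needing intravenous fluids, renal insufficiency or Grade 3 or higher rigors/chills, which "in the absence of an obvious infectious cause are to be reported as a SAE" (6.3.1.1).

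**Chemotherapy.** Section 6.3.1.16, which covers carboplatin and vincristine, designates no event as serious. On hypersensitivity it says "Carboplatin allergies should be documented as an adverse event in the eCRF".

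**Common to both arms.** Section 6.3.1.17 has confirmed potential drug-induced liver injury reported as an SAE. Section 6.1 defines study drug to include carboplatin and vincristine, so that rule reaches both arms.

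**The concern.** An SAE table by arm is readable as a comparison only if seriousness is ascertained alike in both arms. Here one arm is counted under Section 8.2.1 plus a list, and the other essentially under Section 8.2.1 alone. An asymptomatic LVEF fall seen on a scheduled echocardiogram need not meet any Section 8.2.1 criterion. On dabrafenib/trametinib it enters the SAE table because it is named. On chemotherapy the same finding enters only if the investigator judges that it meets a general criterion. Part of any between-arm difference in SAE incidence could then come from labelling rather than harm, in a trial whose randomised safety comparison is meant to inform later treatment recommendations (Section 2.2).

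**Working it through.** The protocol states no figure on this point, so there is none to reproduce. The check compares texts and then bounds the possible size.

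**1. Can the same finding arise in both arms?** Yes. Echocardiography is scheduled at weeks 5, 16, 32 and 48 in Table 7-1 (dabrafenib/trametinib) and in Table 7-3 (chemotherapy). After week 48 the schedules part: weeks 72, 88 and onward in Table 7-1; week 56 and end of treatment in Table 7-3.

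**2. Which designated events add to Section 8.2.1?**

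| Designated event | Likely serious under 8.2.1 anyway? |
|---|---|
| Asymptomatic LVEF fall (>10% absolute and below LLN) | Not necessarily; clearest excess |
| RPED, where Grade 1 is asymptomatic (Table 6-20) | Not necessarily at Grade 1; lesser example |
| Cutaneous squamous cell carcinoma | Depends on the case |
| Other malignancy, retinal vein occlusion, complicated pyrexia | Often, as medically significant or through hospitalisation |
| Potential drug-induced liver injury | Designated in both arms, so no imbalance |

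**3. What do the protocol's own combination data allow?** Section 1.2.3.1 reports 12 children on dabrafenib with trametinib. Two had five possibly related SAEs in total: ejection fraction decrease in both, and one each of nausea, vomiting and pyrexia.
- Patients with an ejection-fraction SAE: 2/12 = 16.7%, exact (Clopper-Pearson) 95% CI 2.1% to 48.4%.
- Nausea and vomiting are not designated events, and they occurred in these same two patients. At least one of the two is therefore an SAE patient whatever the LVEF rule says.
- The most that LVEF alone could add at patient level is 1/12 = 8.3%.
- LGG dabrafenib/trametinib arm: 102 × 2/3 = 68 patients. If the data carried over, 68 × 1/12 = 5.7, about 6 patients. The lower limit is zero, because the events may have met a general criterion anyway.

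**4. Illustration under assumed rates.** Let *b* be the true SAE rate under Section 8.2.1 in both arms, and *a* the share of otherwise SAE-free dabrafenib/trametinib patients counted through designation alone. The tabulated rate is *b* + (1 − *b*)*a*, so the artefact is (1 − *b*)*a*. Neither quantity is in the protocol.

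| *b* | *a* = 5% | *a* = 10% |
|---|---|---|
| 20% | 4.0 points | 8.0 points |
| 30% | 3.5 points | 7.0 points |
| 40% | 3.0 points | 6.0 points |

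**The case against.** The strongest reply is that other planned output already shows most of this. Section 10.5.1.2 summarises all treatment-emergent AEs by preferred term and CTCAE grade regardless of seriousness, and tabulates AESIs, which include cardiac events (Section 8.1.3). Section 10.5.1.4 summarises echocardiogram data, with notable values feeding shift tables. Section 8.1.1, item 7, records which seriousness criteria each event met. Splitting an SAE table is ordinary SAP content, and the SAP is not at hand. All of this is fair, and it limits the consequence for LVEF. It leaves the SAE table itself unequal. Nor is recording the criteria met enough: a site reporting a designated event may tick medically significant, and later analysis could not then separate it.

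It can also be said that the RPED and malignancy sentences are not themselves restricted to one regimen; only their section headings are. That is why asymptomatic LVEF fall, limited by the table's own title, is the firm example.

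Three stronger readings are tempting, and the protocol does not support them:
- *The arms work under two different definitions, and nothing is designated on chemotherapy.* Section 8.2.1 governs both arms, and potential drug-induced liver injury is designated for both. Carboplatin reactions are not shut out of the SAE table: Section 6.3.1.16.5 has moderate to severe ones observed in hospital overnight, so many could qualify under Section 8.2.1.
- *About 11 of 68 patients (68 × 2/12) would be SAE patients by definition.* That ignores the non-designated SAEs in the same two patients.
- *Pyrexia SAEs in earlier paediatric studies add to the excess.* Those reports do not say that the pyrexia was complicated in the sense of Section 6.3.1.1, and complicated pyrexia would often qualify anyway.

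**Conclusion.** The asymmetry is in the text, and the by-arm LGG SAE table inherits it. The table can overstate SAE incidence on dabrafenib/trametinib relative to chemotherapy, most clearly through asymptomatic LVEF decrease. The bias runs against the experimental arm, so it cannot by itself make that arm look safer. It touches a descriptive secondary safety table; formal testing covers ORR, then PFS and OS (Section 10.5), and none of these is affected.

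The size cannot be determined. The figure of at most about 6 of 68 concerns LVEF alone. It assumes that 12 patients in another study, whose SAE rules are not shown, represent this trial, and it rests on possibly related SAEs only. The true excess could be near zero. This is a cheap improvement to a secondary comparison, not a flaw in the trial's main conclusion.

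**What to change.** Leave the planned SAE table and the expedited reporting of designated events unchanged. Add to Section 10.5.1.2 a supplementary LGG between-arm SAE tabulation on a common basis, with two parts:

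1. SAEs that meet a Section 8.2.1 criterion in their own right, with those reported only because Section 6.3.1 designates them shown on a separate line. This needs a protocol-designated-only flag on the SAE form, since such events may otherwise be recorded as medically significant.
2. LVEF falls derived from the echocardiogram data in both arms with the threshold already in Table 6-23 (more than 10% absolute and below the institutional LLN), restricted to the shared visits at weeks 5, 16, 32 and 48. The restriction matters because the schedules diverge afterwards and dabrafenib/trametinib can continue beyond the fixed chemotherapy course.

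The cost is one flag and one extra table. Patient care and reporting timelines do not change.

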#### 10.5.1.3 Laboratory abnormalities

Grading of laboratory values will be assigned programmatically as per NCI Common Terminology Criteria for Adverse Events (CTCAE) version 4.03. The calculation of CTCAE grades will be based on the observed laboratory values only, clinical assessments will not be taken into account.

CTCAE Grade 0 will be assigned for all non-missing values not graded as 1 or higher. Grade 5 will not be used.

For laboratory tests where grades are not defined by CTCAE v4.03, results will be categorized as low/normal/high based on laboratory normal ranges.

The following summaries will be generated separately for hematology, and biochemistry tests:

• Listing of all laboratory data with values flagged to show the corresponding CTCAE v4.03 grades if applicable and the classifications relative to the laboratory normal ranges

For laboratory tests where grades are defined by CTCAE v4.03

- Worst post-baseline CTCAE grade (regardless of the baseline status). Each patient will be counted only once for the worst grade observed post-baseline.
- Shift tables using CTCAE v4.03 grades to compare baseline to the worst on-treatment value

For laboratory tests where grades are not defined by CTCAE y4.03,

• Shift tables using the low/normal/high/ (low and high) classification to compare baseline to the worst on-treatment value.

A listing of laboratory values will be provided by laboratory test, patient, and study day. A separate listing will display notable laboratory abnormalities (i.e., newly occurring CTCAE grade 3 or 4 laboratory toxicities).

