# 6.1.2 Carboplatin and Vincristine Dosing Regimen

Carboplatin and vincristine will be supplied locally as commercially available and labelled accordingly to comply with legal requirements of each country. Carboplatin and vincristine will be administered as one course of induction (10 weeks of chemotherapy with 2 weeks of rest), followed by 8 cycles of maintenance chemotherapy. Each maintenance cycle is 6 weeks. Maintenance cycles are only given following sufficient recovery of hematologic parameters.

Chemotherapy administration should follow the guidelines below and as per local product labels or SmPC. Please consult local product labels and institutional standards for duration of infusion and flush requirements when administering carboplatin and vincristine.

Local safety laboratory testing to confirm hematologic parameters may be conducted per institutional practice during induction and maintenance phases of chemotherapy prior to dosing when central labs are not scheduled per protocol or when central lab results will not be available prior to dosing. Results will be collected in the eCRF.

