# 7.2.2.8 Laboratory evaluations

A central laboratory will be used for analysis of all specimens collected. Details on the collections, shipment of samples and reporting of results by the central laboratory are provided to investigators in the laboratory manual.

Central laboratory results should be used to determine study eligibility, however if there is an immediate need to determine study eligibility and commence treatment on study, then local lab result may be used for assessment of eligibility. In this case, central laboratory samples should still be collected for evaluation. Sites do not need to wait for the results of centrally-analyzed laboratory assessments when an immediate clinical decision needs to be made, and in those cases locally unscheduled testing may be performed.

For LGG patients receiving carboplatin plus vincristine, local laboratory results can be used as required during chemotherapy when a central lab is not scheduled per Visit Evaluation Schedule (Table 7-1, Table 7-2 or Table 7-3) or when central lab results will not be received in time for dosing. Novartis must be provided with a copy of the local laboratory's certification (if applicable), and a tabulation of the normal ranges and units of each parameter collected in the eCRF. Any changes regarding normal ranges and units for laboratory values assessed during

the study must be reported via an updated tabulation indicating the new effective date. Additionally, if at any time a patient has laboratory parameters obtained from a different (outside) laboratory, Novartis must be provided with a copy of the certification and a tabulation of the normal ranges and units for this laboratory as well. The investigator is responsible for reviewing all laboratory reports for patients in the study and evaluating any abnormalities for clinical significance.

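### LGG hematology is summarised by worst grade per arm although blood counts are sampled more often on chemotherapy, so the between-arm comparison is confounded by unequal sampling

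*Protocol*

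**What the plan says.** Protocol 10.5.1.3 fixes two laboratory summaries for tests with CTCAE grades. One is "Worst post-baseline CTCAE grade (regardless of the baseline status). Each patient will be counted only once for the worst grade observed post-baseline". The other is "Shift tables using CTCAE v4.03 grades to compare baseline to the worst on-treatment value". On which values are graded it says only that "The calculation of CTCAE grades will be based on the observed laboratory values only". It does not separate central from local results, or scheduled from unscheduled ones.

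On grouping, 10.5.1 states: "For the LGG cohort the data will be analyzed by treatment arm". The LGG objective in the Protocol summary is comparative: "Evaluate the safety and tolerability of dabrafenib in combination with trametinib versus carboplatin with vincristine".

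The sampling comes from the visit schedules and the chemotherapy sections:

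- **Table 7-1 (D+T):** hematology at screening, Weeks 1, 5, 8, then every 8 weeks to Week 56, every 16 weeks after that, and end of treatment. Nothing at Weeks 2 to 4.
- **Table 7-3 (chemotherapy):** central hematology at screening, Weeks 1 to 5, 8, then every 8 weeks to Week 56, and end of treatment. A separate row for local laboratory tests runs through chemotherapy and is marked for database entry. Table 7-1 has no such row.
- **Section 6.1.2:** "Local safety laboratory testing to confirm hematologic parameters may be conducted per institutional practice during induction and maintenance phases of chemotherapy prior to dosing", with results collected in the eCRF.
- **Sections 6.1.2.2 and 6.3.1.16.1:** counts must have recovered before each of 8 maintenance cycles and are repeated every 7 days while low.
- **Section 7.2.2.8:** for the chemotherapy arm, "local laboratory results can be used as required during chemotherapy when a central lab is not scheduled per Visit Evaluation Schedule".

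Central chemistry has the same schedule in both arms to Week 56, so the issue is mainly hematology.

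**The concern.** A worst value is a maximum over the samples taken. With the same underlying toxicity, the arm with more blood counts will show more patients at a high grade, because short cytopenias are more likely to coincide with a draw. Here the denser sampling is in the control arm, so to Week 56 the unequal ascertainment favours D+T.

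The table serves a stated comparative objective, and neutropenia is an adverse event of special interest (8.1.3). A reader who sees worst hematology grade side by side by arm will take the difference as a difference in toxicity. The protocol gives no information in that table from which the sampling part could be judged.

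**Working it through.** The protocol states no figure for this point, so there is nothing to reproduce. The check counts the samples and then asks how far a worst-grade table would differ between arms if the true risk were the same.

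**Step 1. Post-baseline counts, taking Week 1 as baseline.** Maintenance cycles start at Weeks 13, 19, 25, 31, 37, 43, 49 and 55 if nothing is delayed (Table 7-3).

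- D+T: Weeks 5, 8, 16, 24, 32, 40, 48, 56 = 8.
- Chemotherapy, central only: Weeks 2, 3, 4, 5 plus 8, 16, ..., 56 = 4 + 7 = 11.
- Chemotherapy, central plus one count at each cycle start: 11 + 8 = 19 (no cycle start falls on a central week).
- Chemotherapy, central plus a count at every dosing week: dosing weeks are 10 + 8 × 4 = 42. Dropping Week 1 leaves 41, and adding central Weeks 24 and 48, which fall in rest weeks, gives 43.
- Chemotherapy, weekly to Week 60: 59.

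The first two lines are the scheduled central counts. The third adds the pre-cycle counts that are required. The last two depend on institutional practice.

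**Step 2. Chance that at least one event is recorded.** With k samples and the same per-sample probability p in both arms, P = 1 − (1 − p)^k. The documents give no p, so a range is shown.

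| p (assumed) | D+T, k=8 | Chemo, k=11 | k=19 | k=43 | k=59 |
|---|---|---|---|---|---|
| 1% | 7.7% | 10.5% | 17.4% | 35.1% | 44.7% |
| 2% | 14.9% | 19.9% | 31.9% | 58.1% | 69.6% |
| 5% | 33.7% | 43.1% | 62.3% | 89.0% | 95.2% |

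For example, 1 − 0.98^8 = 14.9% and 1 − 0.98^19 = 31.9%.

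**Step 3. Episodes that last.** Step 2 treats samples as independent. A simulation of 40,000 patients per scenario, with constant weekly onset and a true incidence of about 40% in both arms, relaxes that. Onset rate and duration are again assumptions.

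| Episode length | D+T, 8 | Chemo, 11 | 19 | 43 |
|---|---|---|---|---|
| 1 week | 6.7% | 9.1% | 15.1% | 31.1% |
| 2 weeks | 12.9% | 15.1% | 23.6% | 36.2% |
| 4 weeks | 23.3% | 25.0% | 34.9% | 40.3% |

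With central values only, the gap is small. It widens as local counts are added and narrows, relative to the true rate, as episodes lengthen.

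**Step 4. Effect of restricting the visits.** At the visits common to both arms the count is 8 against 8 and the sampling gap disappears. Restricting to central values without restricting the visits leaves 8 against 11, because Weeks 2 to 4 are sampled only on chemotherapy.

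**The case against.** The strongest reply is that the large figures need local values to enter the table, and the protocol does not say that they do. Section 7.2.2.8 makes the central laboratory the default and gives local results a role in dosing decisions. Collection in the eCRF does not settle what is tabulated, and choosing the data source for a table is commonly left to the SAP. This stands: central-only is a fair reading, and the gap is then small. It does not vanish, and 10.5.1.3 as worded (observed values, with a listing of all laboratory data) more naturally includes local results.

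Several further points also stand:

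- Most pre-dose counts are permitted and not required, so 43 or 59 is a possibility and not the plan.
- D+T continues beyond Week 56 with 16-weekly counts, while chemotherapy ends at about Week 60, so D+T accumulates later chances of a worst value.
- Each pyrexia event calls for a work-up that should include a full blood count (Table 6-16), and pyrexia was reported in 58% of the 12 pediatric combination patients in 1.2.3.1.
- The laboratory tables are descriptive, and adverse events of special interest are tabulated separately from adverse-event data (10.5.1.2).

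A common-visit table has its own weakness: it discards the 7-day repeats that document cytopenias on chemotherapy. That argues against making it the only comparison. It is not shown that these visits systematically miss chemotherapy toxicity. Weeks 16, 24, 32, 40, 48 and 56 fall in weeks 4, 6, 2, 4, 6 and 2 of undelayed maintenance cycles, and Weeks 5 and 8 fall in induction.

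**Conclusion.** The point holds as confounding by unequal sampling. The protocol itself fixes the worst-value summary, the grouping by arm and the unequal schedules, and the direction to Week 56 favours D+T. At an assumed equal 2% per-sample probability the gap is 14.9% against 19.9% with central values only. If local values enter, the chemotherapy figure is 31.9% with 19 counts and 58.1% with 43. These rates are assumptions, and the net size after longer D+T exposure and pyrexia work-ups cannot be derived from the document.

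A reader might infer that sampling frequency determines the hematology comparison, or that cytopenias are nearly always caught on chemotherapy and mostly missed on D+T. The document does not support either. Section 2.1 lists hematologic suppression among the toxicities of carboplatin and vincristine, so part of any difference will be a true drug effect. Nor does the protocol require a count before every chemotherapy dose.

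**What to change.** In 10.5.1.3:

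1. Keep the planned worst-grade and shift tables.
2. For LGG hematology, add a supportive between-arm version of both, restricted to scheduled central values at the common post-baseline visits: Weeks 5, 8, 16, 24, 32, 40, 48 and 56.
3. State whether local and unscheduled values enter the all-values tables.
4. Show the number of counts per patient by arm, and footnote that the all-values tables are subject to unequal sampling.

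The cost is a few sentences and one extra set of tables, with no new data. The common-visit version will miss some true nadirs, possibly more on chemotherapy, so it supplements the planned tables and does not replace them.
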